6.3 Interim Analysis

No interim analysis is planned for this study.

6.4 Multicenter Studies

The study will be conducted at approximately 60 study sites in the US, Canada, and Poland. During the conduct of the study, additional countries and/or sites may be added if necessary.

	STATISTICAL ANALYSIS PLAN, Version 3.0
Protocol Number: ARQ-151-311	Sponsor: Arcutis Biotherapeutics, Inc.

Sites with less than 16 subjects in the ITT population will be pooled within a country:

- a. Sites with less than 16 subjects will be ordered from lowest to highest in terms of number of ITT subjects. In case of ties, the ordering for tied sites will be determined according to the site identification number (from smallest to largest).
- b. Sites will be combined beginning at the smallest until the resulting pooled site contains at least 16 ITT subjects with at least 1 subject in each treatment group. The sites pooled in this way will be considered as a single site in the statistical analyses.
- c. The process described above will resume for the remaining sites not meeting the criterion of at least 16 ITT subjects with at least 1 subject in each treatment group. If the final set of pooled sites does not meet the criterion of at least 16 ITT subjects with at least 1 subject in each treatment group, the final set will be pooled with the preceding pooled site.
- d. If there is only one site with less than 16 ITT subjects with at least 1 subject in each treatment group, then this site will be combined with the site with the second lowest number of subjects. As above, in the case of ties, the ordering for tied sites will be determined according to the site identification number (from smallest to largest).

As a sensitivity analysis of different pooling strategy, sites that have randomized less than 50% of the number of randomized subjects at the site with the largest number of randomized subjects, those sites will be pooled within each country. The sensitivity analysis of pooling strategy will be applied for the primary endpoint only.

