4.6 WI-NRS Population

WI-NRS population will be a subset of the ITT population among subjects ≥ 12 years old with average weekly baseline WI-NRS score ≥ 4 .

The subjects in WI-NRS population are those:

1. Completed at least 4 of 7 evaluable daily WI-NRS questionnaires during the last 7 days of the Screening period;
2. Have a mean baseline WI-NRS score ≥ 4.0 , defined as the average of all non-missing scores reported during the last 7 days of the Screening period if at least 4 of 7 evaluable daily WINRS questionnaires available. If 4 or more evaluable daily questionnaires are missing, then the data will be treated as missing.

All subjects will be analyzed according to the treatment group and stratum to which they were randomized.

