12.1.3 Primary Endpoint Analysis

For the primary analysis, missing vIGA-AD scores will be imputed using multiple imputation as described in Section 6.2.1. These imputations will result in a minimum of 25 to a maximum of 250 complete analysis datasets, depending on the number of imputed monotone datasets that are required.

Percentages of subjects having a vIGA-AD Success (refer to Section 12.1.1) will be presented by visit and treatment group based on multiply imputed data in the ITT population along with a 95% Wilson CI. The common MH odds ratio and common MH proportion difference, adjusted for the randomization factors (i.e., randomized vIGA-AD score and pooled study site) will also be provided along with their common associated 95% CIs. Additionally, count and percentage of subjects having a vIGA-AD success, count and percentage of subjects in each category of the vIGA-AD scale, and descriptive statistics for the vIGA-AD scores, change in vIGA-AD score from

	STATISTICAL ANALYSIS PLAN, Version 3.0
Protocol Number: ARQ-151-311	Sponsor: Arcutis Biotherapeutics, Inc.

baseline and percent change in vIGA-AD score from baseline will be presented by visit and treatment group based on observed data in the ITT population.

The primary endpoint (vIGA-AD Success at Week 4) will then be analyzed using multiple imputation CMH test stratified by the randomization factors. To do so, a CMH analysis will be performed separately for each of the complete multiply imputed analysis data sets, and results will be combined into one multiple imputation inference using the methodology described in Section 6.2.1. Statistical significance will be concluded at the 5% significance level (2-sided). Should the odds ratio be not estimable for at least one multiply imputed dataset, the conclusion of the study will be based on the p-value obtained from a MH test, stratified by the randomization factors, for the common MH proportion difference at Week 4.

The following sensitivity analyses to the primary analysis of the primary endpoint will be performed:

- Multiply-imputed data (refer to Section 6.2.1) on mITT population (refer to Section 4.2) and
- Tipping Point analysis (refer to Section 6.2.3) on ITT population.
- Non-responder imputation (refer to Section 6.2.2) on ITT population.
- Observed data on ITT population (refer to Section 4.1).
- Observed data on PP population (refer to Section 4.3).

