endpoint family 1, comprised of the 4-point reduction on the average weekly WI-NRS at Week 4, Week 2 and Week 1, and secondary endpoint family 2, comprised of the EASI-75 at Week 4, vIGA-AD of ‘clear’ or ‘almost clear’ at Week 4, vIGA-AD of success at week 2 and week 1, vIGA-AD of ‘clear’ or ‘almost clear’ at Week 2 and Week 1. The analysis of secondary endpoint family 1 will be performed as described for the primary efficacy endpoint (refer to Section 12.1.3) but based on the WI-NRS population (refer to Section 4.6) and an alpha level of 0.03 will be used to test these endpoints sequentially as described in Section 6.5. Similarly, the analysis of secondary endpoint family 2 will be performed as described for the primary efficacy endpoint (refer to Section 6.2.1) based on the ITT population (refer to Section 4.1) but an alpha level of 0.02 will be used to test these endpoints sequentially as described in Section 6.5.

Secondary Endpoint Family 1 ($\alpha=0.03$, hierarchical testing)

- In subjects ≥ 12 years old with baseline WI-NRS ≥ 4 , achievement of at least a 4-point reduction in the average weekly WI-NRS at Week 4
- In subjects ≥ 12 years old with baseline WI-NRS ≥ 4 , achievement of at least a 4-point reduction in the average weekly WI-NRS at Week 2
- In subjects ≥ 12 years old with baseline WI-NRS ≥ 4 , achievement of at least a 4-point reduction in the average weekly WI-NRS at Week 1

Secondary Endpoint Family 2 ($\alpha = 0.02$, hierarchical testing)

- Achievement of at least a 75% reduction in the Eczema Area and Severity Index at Week 4 (EASI-75)
- vIGA-AD of ‘clear’ or ‘almost clear’ at Week 4
- vIGA-AD Success at Week 2
- vIGA-AD Success at Week 1
- vIGA-AD of ‘clear’ or ‘almost clear’ at Week 2
- vIGA-AD of ‘clear’ or ‘almost clear’ at Week 1

For the secondary efficacy endpoint of vIGA-AD Success at Week 4 based on the vIGA-AD moderate ITT population, the following sensitivity analyses to the primary analysis of this efficacy endpoint will be performed if and only if the hierarchical testing procedure (refer to Section 6.5) allows it:

- Tipping Point analysis (refer to Section 6.2.3) on vIGA-AD moderate ITT population.

	STATISTICAL ANALYSIS PLAN, Version 3.0
Protocol Number: ARQ-151-311	Sponsor: Arcutis Biotherapeutics, Inc.

- Non-responder imputation (refer to Section [6.2.2](#)) on vIGA-AD moderate ITT population.
- Observed data on vIGA-AD moderate ITT population.

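### Family 1 reuses site pools built on ITT counts, so in the WI-NRS population a share of the site-by-severity strata, mainly Mild, hold one arm only and add nothing to the CMH tests

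*SAP*

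**What the plan says.** **Pooling.** SAP 6.4 states: "Sites with less than 16 subjects in the ITT population will be pooled within a country". Steps a to d require each pool to reach 16 ITT subjects with at least one in each arm, and then "The sites pooled in this way will be considered as a single site in the statistical analyses". The same section gives the scale: "The study will be conducted at approximately 60 study sites in the US, Canada, and Poland".

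**Family 1.** SAP 12.2 states: "The analysis of secondary endpoint family 1 will be performed as described for the primary efficacy endpoint", "but based on the WI-NRS population (refer to Section 4.6) and an alpha level of 0.03 will be used". The primary analysis in 12.1.3 is a CMH analysis whose estimates are "adjusted for the randomization factors (i.e., randomized vIGA-AD score and pooled study site"), and whose test is stratified by the same two factors.

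**Population.** Under SAP 4.6, "WI-NRS population will be a subset of the ITT population among subjects" aged 12 or older with a mean weekly baseline WI-NRS of at least 4. Members must also meet a diary condition: "Completed at least 4 of 7 evaluable daily WI-NRS questionnaires during the last 7 days of the Screening period". Neither document says how many subjects this will be.

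**Clauses that might have helped.**
- The alternative pooling in 6.4 is limited to the primary endpoint.
- The unstratified option for over-stratification in 12.4 belongs to the subgroup analyses.
- The switch to the proportion-difference test in 6.2.1 and 12.1.3 applies only when the common odds ratio cannot be estimated. A few one-arm strata do not cause that.

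**The concern.** The safeguard of 16 subjects with both arms is checked in the full randomized set. Family 1 then uses the same pools after removing children under 12, subjects with milder itch and subjects with sparse diaries, and splits what is left by severity. Nothing in the plan checks that the resulting cells still hold both arms.

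A stratum with only one arm has observed minus expected equal to zero and variance equal to zero. It therefore drops out of the CMH statistic, and its subjects carry no information about treatment.

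What is at stake is power. Under SAP 6.5, Family 1 is tested in sequence at 0.03 (Weeks 4, 2, 1), and all three tests must succeed before 0.03 is added to the 0.02 reserved for Family 2. SAP 5.1 gives no power or sample size for Family 1, so the margin available to absorb a loss is unknown.

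**Working it through.** **1. The plan's own figure.** None exists for Family 1. The nearest is SAP 5.1: 650 subjects, 2:1, 37% vs 22%, two-sided 0.05, about 95% power. On the log-odds-ratio scale:
- ln[(0.37 × 0.78)/(0.63 × 0.22)] = ln 2.08 = 0.733
- SE = √[1/(216.7 × 0.22 × 0.78) + 1/(433.3 × 0.37 × 0.63)] = 0.192
- power = Φ(0.733/0.192 − 1.96) = 96.9%

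This is within 2 points of the stated figure. The ordinary two-proportion formula gives 97.9%. The basic inputs are therefore consistent, but they say nothing about itch response.

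**2. One pool by hand.** From SAP 5.1, 490/650 = 75% are Moderate. A minimum pool of 16 holds about 12 Moderate and 4 Mild subjects. If half of ITT enters the WI-NRS population (assumption), about 6 and 2 remain. With simple 2:1 allocation, the chance that a stratum of m subjects has one arm only is (2/3)^m + (1/3)^m:
- Moderate, m = 6: 0.088 + 0.001 = 9%
- Mild, m = 2: 0.444 + 0.111 = 56%

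The problem sits mainly in the Mild cells, which hold few subjects each.

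**3. Simulation of the 6.4 rule.** Assumptions not in the documents: uneven site sizes, blocks of 3, WI-NRS membership independent of site, vehicle response 15%, and an effect giving about 80% unstratified power at 0.03. From the documents: 650 subjects, 60 sites, 25% Mild, 2:1. There were 1,500 trials per setting, with a simulation error of about 1 point on power. Information is the sum of n1·n0/n over strata, divided by N × 2/9.

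| WI-NRS share of ITT | Subjects in one-arm strata | After re-pooling | Information, plan → re-pooled | Power, plan → re-pooled |
|---|---|---|---|---|
| 35% | 14% | about 3% | 82% → 92% | 71% → 76% |
| 50% | 7% | about 2% | 89% → 94% | 74% → 76% |
| 65% | 4% | about 2% | 93% → 95% | 78% → 79% |

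**4. A second simulation with varied assumptions** (60 sites, two site-size distributions, blocks of 3 or 6, a country split of about 75/13/12%, 400 runs per setting). Ranges run across the settings.

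| WI-NRS share of ITT | One-arm strata | Subjects lost | Lost after re-pooling |
|---|---|---|---|
| 70% | 10–13% | 2.6–3.9% | 1.3–2.1% |
| 50% | 19–22% | 6–8% | 1.9–2.6% |
| 40% | 25–29% | 10–13% | 2.3–3.1% |
| 30% | 34–38% | 16–19% | 2.9–3.3% |

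At 50%, 35–41% of Mild strata are one-arm, against 3–4% of Moderate strata. In the full ITT population, 3–6% of strata are already one-arm, at a cost of 0.6–1.5% of subjects. With 40 sites, the loss at 50% is 4–6% of subjects. At 50%, with assumed rates of 35% vs 20%, re-pooling gains about 2–3 power points. The two simulations agree.

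**5. Moderate ITT.** SAP 12.2 stratifies this endpoint by pooled site only. A 16-subject pool keeps about 12 Moderate subjects, and the one-arm chance is (2/3)^12 = 0.8%. There is no practical loss.

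**The case against.** **One prespecified set of pools for every analysis is a legitimate choice.** This stands. The 6.4 criterion is written for ITT subjects per pooled site. It promises nothing for subsets or for site-by-severity cells, so a reader who infers that the SAP breaks its own rule goes too far.

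**The gain is small.** This also stands. At 65% of ITT it is within simulation error. The effect was tuned to about 80% power. If unstratified power were 95%, the information figures above imply gains of about 3, 1.4 and 0.5 points (90.1 to 93.2, 92.3 to 93.7 and 93.4 to 93.9). The information measure also ignores precision gained from finer strata when response varies by site. With a between-site log-odds SD of 1.0, the gain at 50% falls to about 1 point, within error, though at 35% it remains about 3 points.

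**The cause is the crossing with Mild severity, which re-pooling leaves in place.** This is largely right: 6–10% of strata remain one-arm after re-pooling. In a smaller simulation (600–800 runs), keeping the ITT pools and dropping severity did about as well as re-pooling: power of 73% vs 72% at both 50% and 35% of ITT, against 70% and 69% under the plan. Re-pooling nevertheless recovers most of the lost subjects and keeps both randomization factors.

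**Section 6.2.1, step 3, may already drop severity.** It speaks of adjusting for pooled site alone for the secondary endpoint, in the singular. In context this is the Moderate endpoint, and 12.2 sends Family 1 to 12.1.3. If the clause did cover Family 1, the loss would be under 1% at 50% of ITT and 4–6% at 30%.

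**Conclusion.** The mechanism follows from the SAP text: pools fixed on ITT counts, reused in a restricted population, crossed with severity, with no collapsing rule. The size rests on assumptions, chiefly the unstated WI-NRS share. About 14%, 7% or 4% of subjects are lost at 35%, 50% or 65% of ITT, and re-pooling is worth roughly 5, 1 to 2, or 1 points of power. Clustering of younger children at particular sites would make the loss larger.

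Four stronger readings are tempting, and the documents do not support them:
- **That the WI-NRS population is far smaller than ITT, or that most strata are lost.** Its size is not given. A high one-arm frequency is a feature of the Mild cells, or of a share of about 40% or less.
- **That the test is biased or its type I error inflated.** One-arm strata simply add nothing.
- **That failure in Family 1 closes off Family 2.** Under SAP 6.5, Family 2 is still tested at 0.02. Only the additional 0.03 is forgone.
- **That the Moderate gatekeeper is affected.** It is stratified by site alone, and the one-arm chance for a typical minimum pool is about 0.8%.

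This is a cheap improvement in efficiency, of modest value unless the WI-NRS population is well under half of ITT.

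**What to change.** Add one sentence to SAP 6.4 before unblinding: for the Family 1 analyses, steps a to d are applied to counts in the WI-NRS population, so that each pooled site has at least 16 WI-NRS subjects and at least one in each arm. Leave the Moderate ITT analysis as it is. It would also help to state in 6.2.1, step 3, that the site-only adjustment refers to the Moderate endpoint.

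The cost is that sentence and a second run of the pooling program. There are two downsides to record:
- **Different site factors.** The Family 1 pools will differ from the ITT pools and need not nest within them. Pooled site is also a predictor in the imputation model (6.2.1, step 2), and WI-NRS is imputed on all randomized subjects, so imputation and analysis would use different site groupings.
- **Residual one-arm cells.** The rule works per pooled site, not per site-by-severity cell, so some Mild strata will still hold one arm and about 2–3% of subjects will still be lost.

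Stratifying Family 1 by severity alone would lose essentially no subjects, but it gives up site as a stratification factor.

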6.5 Multiple Comparisons/Multiplicity

To control for familywise type I error at level of 0.05, the secondary endpoint of vIGA-AD Success at Week 4 for subjects with vIGA-AD score of ‘Moderate’ at randomization will only be tested if the primary endpoint demonstrates statistical significance. In addition, the remaining secondary endpoints will be inferentially tested only if the primary and the secondary endpoint (vIGA-AD Success at Week 4 for subjects with vIGA-AD score of ‘Moderate’ at randomization) comparisons are statistically significant using hierarchical testing procedure by partitioning of alpha.

Upon successful demonstration of statistical significance for the primary and above secondary endpoint, the remaining endpoints will be grouped into secondary endpoint family 1, comprised of the 4-point reduction on the WI-NRS endpoint, at Week 4, Week 2 and Week 1, and secondary endpoint family 2, comprised of the endpoints of EASI-75 at Week 4, vIGA-AD of ‘clear’ or ‘almost clear’ at Week 4, vIGA-AD of success at Week 2 and Week 1, vIGA-AD of ‘clear’ or ‘almost clear’ at Week 2 and Week 1. An alpha level of 0.03 will be used to test the endpoints in the secondary endpoint family 1 sequentially. An alpha level of 0.02 will be used to test the endpoints in secondary endpoint family 2 sequentially.

	STATISTICAL ANALYSIS PLAN, Version 3.0
Protocol Number: ARQ-151-311	Sponsor: Arcutis Biotherapeutics, Inc.

In addition to the partitioning of the overall 0.05 alpha into two families, the Fallback Method will be applied. The fallback method is a modification of the fixed-sequence method, providing opportunity to test an endpoint later in the sequence even if an endpoint tested early in the sequence has failed to show statistical significance. The order of the endpoints remains important. The appeal of the fallback method is that if an endpoint later in the sequence has a robust treatment effect while the preceding endpoint is unsuccessful, there is a modest amount of alpha retained as a fallback to allow interpretation of that endpoint without inflating the Type I error rate. Applying the fallback method begins by dividing the total alpha (not necessarily equally) among the endpoints and maintains a fixed sequence for the testing. In this study, the Fallback Method will be applied to the fixed sequence of testing Family 1, and then Family 2.

As the testing sequence progresses, a successful test preserves its assigned alpha as “saved” (“unused” or “accumulated”) alpha that is passed along to the next test in the sequence, as is the case for the sequential method. This accumulated alpha is added to the prospectively assigned alpha (if any) of that next endpoint and the summed alpha is used for testing that endpoint. Thus, as sequential tests are successful, the alpha accumulates for the endpoints later in the sequence; these endpoints are then tested with progressively larger alphas.

[figure not shown]
In this study, the Fallback Method will be applied following this sequence:

Family 1: Testing will proceed at the 0.03 level sequentially within Family 1. Should all 3 endpoints in Family 1 be statistically significant at the 0.03 level, then the full 0.03 alpha will be carried to Family 2. Family 2 would then be tested at the full ($\alpha=0.02+0.03=0.05$).

Should, anywhere during the sequential testing of Family 1, there is a p-value >0.03 , the testing within Family 1 will stop, and no additional alpha can be carried over to Family 2.

	STATISTICAL ANALYSIS PLAN, Version 3.0
Protocol Number: ARQ-151-311	Sponsor: Arcutis Biotherapeutics, Inc.

Figure 2 Multiple Testing Scheme

Achievement of vIGA-AD success is a score of "clear" or "almost clear" plus a 2-grade improvement from baseline.

WI-WRS Success is a 4-point reduction in WI-NRS among subjects ≥ 12 years old with WI-NRS ≥ 4 at baseline.

EASI-75: achievement of at least a 75% reduction in the Eczema Area and Severity Index

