5.7 Statistical Tests

Unless otherwise specified, all statistical tests will be two-sided and will be performed with a significant level of 0.05. Confidence intervals (CIs) will be two-sided with 95% coverage.

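### SAP 6.5 leaves 0.02 of alpha unused when Family 1 stops and all six Family 2 endpoints succeed; a return path conditional on all six would use it within the 0.05 familywise level

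*SAP*

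**What the plan says.** SAP 6.5 sets out its purpose: "To control for familywise type I error at level of 0.05". The primary endpoint is tested first. vIGA-AD Success in subjects randomized as Moderate "will only be tested if the primary endpoint demonstrates statistical significance". If both succeed, the remaining secondaries form two families:

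- **Family 1:** 4-point WI-NRS reduction at Weeks 4, 2 and 1. "An alpha level of 0.03 will be used to test the endpoints in the secondary endpoint family 1 sequentially".
- **Family 2:** EASI-75 at Week 4; clear or almost clear at Week 4; vIGA-AD Success at Weeks 2 and 1; clear or almost clear at Weeks 2 and 1. "An alpha level of 0.02 will be used to test the endpoints in secondary endpoint family 2 sequentially".

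The direction of flow is fixed: "In this study, the Fallback Method will be applied to the fixed sequence of testing Family 1, and then Family 2". If all three itch endpoints succeed, "then the full 0.03 alpha will be carried to Family 2", which is then tested at 0.05. If any itch p-value exceeds 0.03, "the testing within Family 1 will stop, and no additional alpha can be carried over to Family 2".

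That last sentence blocks transfer from Family 1 to Family 2. The lack of a path the other way follows from the stop in Family 1 and from the stated sequence. The summary table in 12.5 agrees: it lists Family 2 at 0.02 or 0.05, but Family 1 only at 0.03. Section 12.2 also gives Family 1 only 0.03. Figure 2 could not be seen. Protocol 6.7 has the same 0.03/0.02 split, with Holm in Family 2 and no transfer in either direction.

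**The concern.** Suppose itch at Week 4 gives p = 0.04 and every Family 2 endpoint is then significant at 0.02. Family 1 has stopped, itch at Weeks 2 and 1 is never tested, and the 0.02 that Family 2 has won goes nowhere. Itch at Week 4 cannot be claimed, although the only hypotheses still open are itch hypotheses and the plan allows 0.05 in total. Under 12.2 the sensitivity analyses of these secondaries also run only where the testing procedure allows.

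The sponsor gives itch the larger share of alpha and tests it in a restricted set: age 12 or over, baseline weekly WI-NRS of at least 4, and at least 4 of 7 diary days. SAP 5.1 states no power for it. Alpha that could be used at no loss elsewhere is therefore worth recovering.

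**Working it through.** **Inputs.** From SAP 6.5: familywise level 0.05; Family 1 at 0.03 (3 endpoints); Family 2 at 0.02 (6 endpoints); fixed sequence in each. From SAP 5.7: "all statistical tests will be two-sided and will be performed with a significant level of 0.05". The documents give no itch response rates and no WI-NRS population size, so every power below is an assumption.

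**1. The plan's own figure.** 0.03 + 0.02 = 0.05. Reproduced.

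**2. The current scheme as a closed test.** There are 11 hypotheses (primary, Moderate, 3 itch, 6 Family 2), so 2^11 − 1 = 2,047 intersections. The local level of each is:

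- contains the primary or Moderate hypothesis: 0.05;
- contains itch and Family 2 hypotheses only: 0.03 + 0.02 = 0.05;
- contains Family 2 hypotheses only: 0.02 + 0.03 passed on = 0.05;
- contains itch hypotheses only: 0.03.

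The last group has 2^3 − 1 = 7 members. So 2,040 intersections use the full 0.05 and 7 use 0.03. Error is controlled, and the slack is 0.05 − 0.03 = 0.02 in those 7.

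**3. With the return path.** If the last Family 2 endpoint passes its alpha back to Family 1, the 7 itch-only intersections rise to 0.05 and the other 2,040 are unchanged. No local weight falls anywhere, so every rejection made under the current plan is still made. Simulation (400,000 runs per null case, equal correlation 0, 0.5 or 0.8) gave familywise error of at most 0.0504. The simulation standard error is √(0.05 × 0.95 / 400,000) ≈ 0.0003, so this is consistent with 0.05.

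**4. The all-six condition is essential.** If alpha were returned after EASI-75 alone while Family 2 kept its 0.02, simulated familywise error reached 0.069.

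**5. Upper bound on the gain for itch at Week 4.** The added power is P(0.03 < p ≤ 0.05 and all six Family 2 tests pass at 0.02). This cannot exceed power at 0.05 minus power at 0.03. By normal approximation, power at 0.05 = Φ(2.170 + z(power at 0.03) − 1.960):

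| Assumed power at 0.03 | Power at 0.05 |
|---|---|
| 50% | 58.3% |
| 60% | 67.8% |
| 70% | 76.9% |
| 80% | 85.4% |
| 90% | 93.2% |

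The bound is reached only if Family 2 is certain to succeed.

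**6. Less favourable cases.** Simulated gain in Week 4 itch power, starting from 80%, at correlation 0, 0.5 and 0.8:

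- All six Family 2 endpoints at 90% power each: about 2.8, 2.5 and 2.5 points.
- The two Week 1 endpoints at 50%, the other four at 90%: about 0.9, 0.6 and 0.2 points.

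The gain depends on the starting power. From 50% itch power, with Family 2 standardized effects of 3 to 4, it was 3.2, 4.5 and 6.0 points. With effects of 2 to 3 it was 0.2, 0.8 and 0.7.

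**7. The cost.** With real Family 2 effects and all itch hypotheses null, simulated probability of a false itch claim rose from 0.030 to 0.050 (correlation 0: 0.0301 to 0.0502).

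**The case against.** The strongest reply is that nothing is broken. The SAP names the Fallback Method, says that order matters, and tests itch first with the larger share. One-way flow is part of the procedure it chose, and a loop-back graph is simply another valid procedure. This stands: the point is an available improvement, not a defect.

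Three further objections also stand in part.

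- **A reader might infer that the change has no downside.** That goes too far. No rejection is lost and the familywise level holds, but a false itch claim becomes more likely (0.03 to 0.05) when itch is null and Family 2 is real. The SAP already accepts the mirror case, since Family 2 rises from 0.02 to 0.05 after Family 1 succeeds.
- **A reader might infer that itch is the secondary most likely to miss.** The documents show that the WI-NRS population is a subset, but give no size, response rate or power for it. A 2-grade improvement at Week 1 could equally be the weakest secondary, and if it fails the return path does nothing.
- **The 68/77/85/93% figures could be read as the expected result.** They are best cases. The outcomes come from the same subjects, so correlation is plausible. With correlation 0.5 and all six Family 2 endpoints at 90%, itch power among trials where Family 2 succeeds is already about 90% at 0.03 and becomes about 94%.

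**Conclusion.** The point holds as an optional efficiency gain. SAP 6.5 controls familywise error at 0.05 as stated, and a reading that it is invalid has no support. Its one-way flow leaves 0.02 unused in one situation: Family 1 has stopped and all six Family 2 endpoints are significant at 0.02.

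A return of that 0.02, conditional on all six, is valid and can only add itch rejections. It changes a result only when the failing itch endpoint has 0.03 < p ≤ 0.05. The gain for itch at Week 4 is at most 8.3 points at 50% power, 5.4 at 80% and 3.2 at 90%. From 80%, it is about 0 to 3 points under the less favourable assumptions tried. All of these rest on assumed power, and the smaller figures also on assumed correlation. The reading that no return path exists rests on the text of 6.5 and 12.2 and on the table in 12.5; Figure 2 was not available to confirm it.

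**What to change.** Add to SAP 6.5: *If Family 1 stops and all six Family 2 endpoints are significant at 0.02, the 0.02 is returned and testing of Family 1 resumes at the first non-significant endpoint at 0.05.*

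Then align three places: 12.2 (the Family 1 level and the retest rule, which also governs when the sensitivity analyses run), the summary table in 12.5 (Family 1 at 0.03 or 0.05), and Figure 2 (a path from the last Family 2 endpoint to Family 1, if none is drawn).

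The cost is a few aligned text edits, with no new data or analyses beyond those already planned, plus the higher chance of a false itch claim described above. The rule must be fixed before unblinding; SAP section 1 places this version before database lock and unblinding.
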